2.1.4.3 Laboratory safety variables

Clinical laboratory data consists of blood analysis, including hematology, clinical chemistry, and urinalysis. Clinical laboratory values after conversion will be analyzed into standard international units and international units will be used in all listings and tables.

Blood samples for routine clinical laboratories will be taken at Screening, randomization, Weeks 4, 12 and then every 12 weeks up to the EOT (Week 96, premature treatment discontinuation visit and the time when patient switches to the open label period after a clinical confirmed relapse or high MRI activity whichever comes first) in the double-blind period, and then at transition, Weeks 4, 12 and then every 12 weeks up to the EOT (Week 192 or premature treatment discontinuation visit whichever comes first) in the open-label period. The laboratory parameters will be classified as follows:

- Hematology
 - **Red blood cells and platelets and coagulation:** hemoglobin, hematocrit, mean corpuscular hemoglobin, red blood cell count, platelet count, prothrombin time, activated partial thromboplastin time
 - **White blood cells:** white blood cell count, neutrophils, lymphocytes, monocytes, basophils, eosinophils
- Clinical chemistry
 - **Metabolism:** glucose, cholesterol, triglycerides, total protein, albumin, globulin, albumin/globulin ratio, creatine phosphokinase(CPK), serum amylase and lipase
 - **Electrolytes:** sodium, potassium, chloride, calcium, inorganic phosphorus, bicarbonate, magnesium
 - **Renal function:** creatinine, creatinine clearance, blood urea nitrogen (BUN), uric acid
 - **Liver function:** alanine aminotransferase(ALT), aspartate aminotransferase(AST), alkaline phosphatase, Gamma Glutamyl Transferase(GGT), lactate dehydrogenase (LDH), total bilirubin, direct/indirect bilirubin
 - **Pregnancy test:** Serum β -human chorionic gonadotropin (β -HCG) for pubescent females (NOTE: This test is performed at screening, randomization and then every 12 weeks and EOT in the double-blind period, and then every 12 weeks and EOT in the open-label period)
- Urinalysis - quantitative analyses: pH, ketones, protein, glucose, blood, urobilinogen, bilirubin, microscopic sediment and specific gravity

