2.4.5.3 Analyses of laboratory variables

The summary statistics (including number, mean, median, Q1, Q3, standard deviation, minimum and maximum) of all laboratory variables (central laboratory values and changes from baseline) will be calculated for each visit or study assessment (baseline, each postbaseline time point, last on-treatment and/or minimum and maximum value during the treatment-emergent adverse event period) by treatment group. Mean changes from baseline with the corresponding standard error will be plotted over time (at same time points) in each treatment group for laboratory parameters of primary interest. This section will be organized by biological function.

PCSA will be assessed based on age group at each visit. After subjects turn to be adult, the adult criteria will be applied. The incidence of PCSAs (list provided in [Appendix A](#)) at any time during the treatment-emergent adverse event period will be summarized by biological function and treatment group whatever the baseline level and/or according to the following baseline status categories:

- Normal/missing.
- Abnormal according to PCSA criterion or criteria.

The proportion of patients with key PCSA values at any time during the treatment-emergent adverse event period will also be displayed by duration of exposure for each treatment group.

For parameters for which no PCSA criteria are defined, similar table(s) using the normal range will be provided.

A listing of patients with at least one post-baseline PCSA will be provided and will display the whole profile over time at any time of all parameters of the corresponding biological function. In this listing, baseline, endpoint value and individual values will be flagged when lower or higher than the lower or upper laboratory limits and/or when reaching the absolute limit of abnormality criteria.

Drug-induced liver injury

The liver function tests, namely AST, ALT, alkaline phosphatase, and total bilirubin, are used to assess possible drug-induced liver toxicity. The proportion of patients with PCSA values at any postbaseline visit by baseline status will be displayed by treatment group for each parameter. The proportion of patients with PCSA values at any postbaseline visit will also be displayed by duration of exposure for each treatment group.

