2.5 DATA HANDLING CONVENTIONS

2.5.1 General conventions

The following formulas will be used for computation of parameters.

Demographic formulas

Age = integer part of (date of consent in the double-blind period– date of birth) / 365.25

BMI (in kg/m²) = weight in kg / (height [in m] x height [in m])

Renal function formulas

Creatinine clearance (CrCl) value for children up to 18 years old will be derived from body length and plasma creatinine (Scr) using the updated Schwartz (Bedside Schwartz) equation:

For children/adolescents: CrCl (mL/min/1.73m²) = 0.413 x (height [cm] / Scr [μmol/L]),
where eGFR (estimated glomerular filtration rate) = mL/min/1.73 m²

Creatinine clearance value for adults will be derived using the equation of Cockcroft and Gault:

For males: $crcl(mL/min) = \frac{(140-age) \times weight (kg)}{0.814 \times creatinine (\mu mol/L)}$

For females: $crcl(mL/min) = \frac{(140-age) \times weight (kg)}{0.814 \times creatinine (\mu mol/L)} \times 0.85$

The last height or weight measurement on or before the visit of the creatinine measurement will be used. The age collected at the visit will be used.

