When the date of the first IMP administration is missing, all adverse events that occurred on or after the day of randomization should be considered as treatment-emergent adverse events. The exposure duration should be kept as missing.

The last dose intake should be clearly identified in the case report form and should not be approximated by the last returned package date.

Handling of missing assessment of relationship of adverse events to investigational medicinal product

If the assessment of the relationship to IMP is missing, then the relationship to IMP has to be assumed and the adverse event considered as such in the frequency tables of possibly related adverse events, but no imputation should be done at the data level.

Handling of missing severity of adverse events

If the severity is missing for 1 of the treatment-emergent occurrences of an adverse event, the maximal severity on the remaining occurrences will be considered. If the severity is missing for all the occurrences, a “missing” category will be added in the summary table.

Handling of potentially clinically significant abnormalities

If a patient has a missing baseline he will be grouped in the category “normal/missing at baseline.”

For PCSAs with 2 conditions, one based on a change from baseline value of the double-blind period or a normal range and the other on a threshold value, with the first condition being missing, the PCSA will be based only on the second condition.

For a PCSA defined on a threshold and/or a normal range, this PCSA will be derived using this threshold if the normal range is missing; eg, for eosinophils the PCSA is >0.5 GIGA/L or $>ULN$ if $ULN \geq 0.5$ GIGA/L. When ULN is missing, the value 0.5 should be used.

Measurements flagged as invalid by the laboratory will not be summarized or taken into account in the computation of PCSA values.

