	24 months/2 years to <6 years old (Children)	<22 per minutes >34 per minutes	
	6 to <12 years old (Children)	<18 per minutes >30 per minutes	
	12 to 16/18 years old (Adolescents)	<12 per minutes >20 per minutes	
SaO2	All age ranges	\leq 95%	
Weight	All ranges	\geq 5% weight loss from baseline	Based on identification of trends in the child's growth with a series of visits WHO Multicentre Reference Study Group, 2006; Center for Disease Control. Growth chart 2007

**Criteria for potentially clinically significant abnormalities
For studies in children
(Version 3.0 May 2014)**

Parameter	Age range	PCSA	Comments
Clinical Chemistry			
ALT/SGPT	All age ranges	>3 ULN By distribution analysis: >3 ULN >5 ULN >10 ULN >20 ULN	Ref Molleston JP et al. JPGN 2011; Moritz et al., Pediatrics 1999; Moritz et al., Pediatr Nephrol 2005 ; Sedlacek et al., Seminars in Dialysis 2006) Gong G et al. Clinical Biochemistry 2009; Masilamani et al. Arch Dis Children 2012; Mulberg AE et al. Pediatric Drug Development Concepts and applications. John Wiley & sons, Inc. 2009 Based on normal ranges: 6 to 50 U/L (0-5 days), 5 to 45 U/L (1-19 years)
AST/SGOT	All age ranges	>3 ULN By distribution analysis: >3 ULN >5 ULN >10 ULN >20 ULN	Based on normal ranges: 35 to 140 U/L (0-5 days), 15 to 55 U/L (1-9 years), 5 to 45 U/L (10-19 years)
Alkaline Phosphatase	All age ranges	≥1.5 ULN	Based on normal ranges: 145 to 420 U/L (1-9 years), 130 to 560 U/L (10-11 years), 200 to 495 U/L (Boys 12-13 years), 105 to 420 U/L (Girls 12-13 years), 130 to 525 U/L (Boys 14-15 years), 70 to 130 U/L (Girls 14-15 years), 65 to 260 U/L (Boys 16-19 years), 50 to 130 U/L (Girls 16-19 years)
Total Bilirubin	All age ranges	≥1.3 ULN	CF = mg x 1.7 = μmol Based on normal ranges: <6 mg/dL (Term 0-1 day), <8 mg/dL (Term 1-2 days), <12 mg/dL (Term 3-5 days), <1 mg/dL (Term >5 days)
Conjugated Bilirubin	All age ranges	>35% Total Bilirubin and TBILI≥1.3 ULN	CF = mg x 1.7 = μmol Based on normal range: 0 to 0.4 mg/dL

**Criteria for potentially clinically significant abnormalities
For studies in children
(Version 3.0 May 2014)**

Parameter	Age range	PCSA	Comments
ALT and Total Bilirubin	All age ranges	ALT ≥3 ULN and Total Bilirubin ≥2 ULN	
CPK	All age ranges	≥3 ULN	
Creatinine	Birth/0 to <6 years old (Neonates, Infants, Children)	>53 µmol/L or 0.6 mg/dL	CF = mg x 8.8 = µmol Based on normal ranges: <0.6 mg/dL (0-1 year), 0.5 to 1.5 mg/dL (1 to 16/18 years)
	6 years to <12 years old (Children)	>90 µmol/L or 1.1mg/dL	

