	12 years to 16/18 years old (Adolescents)	>132 µmol/L or 1.5mg/dL	
Creatinine Clearance	All age ranges	50 % of normal <60 mL/min/1.73m ² (After 1 year old)	Based on GFR Bedside Schwartz Formula Based on normal ranges: 20 to 50 (<8 days), 25 to 80 (8 days to 1 month), 30 to 90 (1-6 months), 40 to 115 (6-12 months), 60 to 190 (12-23 months), 90 to 165 (2-12 years), 80-120 (After 12 years)
Uric Acid	All age ranges	<2.0 mg/dL or 119 µmol/L >8.0 mg/dL or 476 µmol/L	CF = mg x 5.95 = µmol Based on normal ranges: 2.4 to 6.4 mg/dL
Blood Urea Nitrogen (BUN)	Birth/0 to 27 days old (Neonates)	≥4.3 mmol/L or 12 mg/dL	CF = g x 16.66 = mmol Based on normal ranges: 3 to 12 mg/dL (NN; 5 to 18 mg/dL (other classes of age)
	28 days/1 month to 16/18 years old (Infants, Children, Adolescents)	≥6.4 mmol/L or 18 mg/dL	
Chloride	All age ranges	≤80 mmol/L or 80 mEq/L ≥115 mmol/L or 115 mEq/L	CF = 1 Based on normal range: 98 to 106
Sodium	All age ranges	≤129 mmol/L or 129 mEq/L ≥150 mmol/L or 150 mEq/L	CF = 1 Based on normal range : 134 to 146
Potassium	Birth/0 to 27 days old (Neonates)	≤3.0 mmol/L or 3.0 mEq/L ≥7.0 mmol/L or 7.0 mEq/L	CF = 1 Based on normal ranges: 3.0 to 7.0 (NN); 3.5 to 6.0 (Infants); 3.5 to 5.0 (>Infants)
	28 days/1 month to 23 months old (Infants)	≤3.5 mmol/L or 3.5 mEq/L ≥6.0 mmol/L or 6.0 mEq/L	
	24 months/2 years to 16/18 years old (Children, Adolescents)	≤3.5 mmol/L or 3.5 mEq/L ≥5.5 mmol/L or 5.5 mEq/L	
Bicarbonate	All age ranges	≤16 mmol/L or 16 mEq/L ≥30 mmol/L or 30 mEq/L	CF = 1 Based on normal range: 18 to 26

**Criteria for potentially clinically significant abnormalities
For studies in children
(Version 3.0 May 2014)**

Parameter	Age range	PCSA	Comments
Calcium total	All age ranges	≤2.0 mmol/L or 8.0 mg/dL ≥2.9 mmol/L or 11.6 mg/dL	CF = mg x 0.025 = mmol Based on normal range: 8.4 to 10.9 mg/dL
Calcium ionized	All age ranges	≤1.0 mmol/L or 4.0 mg/dL ≥1.4 mmol/L or 5.6 mg/dL	CF = mg x 0.025 = mmol Based on normal range: 4.0 to 5.1 mg/dL
Total Cholesterol	All age ranges	>6.20 mmol/L or 240 mg/dL	CF = g x 2.58 = mmol Based on normal ranges: 45 to 182 mg/dL (1-3 years), 109 to 189 mg/dL (4-6 years), 126 to 191 mg/dL (Boys 6-9 years), 122 to 209 mg/dL (Girls 6-9 years), 130 to 204 mg/dL (Boys 10-14 years), 124-217 mg/dL (Girls 10-14 years), 114 to 198 mg/dL (Boys 15-19 years), 125 to 212 mg/dL (Girls 14-19 years)

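### The open-label SAP's creatinine clearance formula for under-18s pairs 0.413 with creatinine in micromol/L; followed literally, values come out about 88-fold too low and essentially every patient is flagged, at baseline too

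*SAP*

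**What the plan says.** SAP section 2.5.1 (General conventions, renal function formulas) gives the clearance formula for children and adolescents as "0.413 x (height [cm] / Scr [μmol/L", names it the updated (Bedside) Schwartz equation, and states the result in mL/min/1.73m². Adults are handled by Cockcroft-Gault, also with creatinine in micromol/L. Age at the visit is used.

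Section 2.1.4.3 lists creatinine clearance among the renal parameters and sets the units: "Clinical laboratory values after conversion will be analyzed into standard international units and international units will be used in all listings and tables".

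Appendix A (criteria for studies in children) flags clearance below 60 mL/min/1.73m². Its comment for that row reads "Based on GFR Bedside Schwartz Formula" and gives normal ranges of "90 to 165 (2-12 years), 80-120 (After 12 years". Its creatinine row gives normal values of "0.5 to 1.5 mg/dL (1 to 16/18 years".

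Section 2.4.5.3 tabulates potentially clinically significant abnormalities (PCSAs) "whatever the baseline level and/or according to the following baseline status categories", the categories being normal/missing and abnormal by the PCSA criterion. It adds: "A listing of patients with at least one post-baseline PCSA will be provided". On missing baselines, section 2.5.2 says "If a patient has a missing baseline he will be grouped in the category" normal/missing. Section 2.4.5 takes the double-blind baseline as the baseline for safety.

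**The concern.** A normal creatinine put into the SAP's formula should return something close to the SAP's normal clearance. As written it returns a value near 1. Because section 2.1.4.3 calls for SI units, a programmer who follows the plan will supply micromol/L, and nothing elsewhere in the SAP rescales the result.

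The outputs at stake are the clearance summaries, the clearance PCSA incidence by baseline status and the PCSA listing in the open-label report. All patients were 10 to 17 at entry (section 1.1), so every baseline clearance falls under this formula. The listing shows the full profile of all parameters of the affected biological function for each flagged patient, so flagging everyone would bury any real renal finding.

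**Working it through.** **Inputs from the documents**

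- Formula: 0.413 × height (cm) / creatinine (micromol/L), SAP 2.5.1.
- Normal creatinine 0.5 to 1.5 mg/dL, Appendix A.
- Conversion, from paired thresholds in Appendix A: 132/1.5 = 88.0 and 53/0.6 = 88.3 micromol/L per mg/dL. A third pair, 90/1.1 = 81.8, is more coarsely rounded. Protocol exclusion criterion E 26 gives 133/1.5 = 88.7.
- Normal creatinine in micromol/L: 0.5 × 88 = 44 to 1.5 × 88 = 132.
- PCSA threshold: below 60 mL/min/1.73m².

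**Assumed:** heights of 120 to 190 cm. The documents give no height distribution.

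**Step 1. Can the formula reproduce Appendix A's normal clearance (90 to 165, or 80 to 120)?** It cannot with micromol/L; with mg/dL the order of magnitude is right.

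| Height, creatinine | As written | With mg/dL (× 88) |
|---|---|---|
| 120 cm, 132 micromol/L | 0.413 × 120/132 = 0.38 | 33.0 |
| 165 cm, 60 micromol/L | 0.413 × 165/60 = 1.14 | 99.9 |
| 190 cm, 44 micromol/L | 0.413 × 190/44 = 1.78 | 156.9 |

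The gap is exactly the unit conversion.

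**Step 2. Could any patient escape the flag as written?** A result of 60 or more needs creatinine of at most 0.413 × height/60. That is 0.83 micromol/L at 120 cm and 1.31 at 190 cm, against a lower normal limit of about 44. Appendix A also words the criterion as 50% of normal (40 to 60 after age 12), but values near 1 fail that reading as well.

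**Step 3. Effect on the planned tables.** Every non-missing baseline is below 60. The normal/missing category then holds only patients with a missing baseline. Essentially every patient with a post-baseline value before age 18 enters the listing.

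**Step 4. The change of equation at age 18.** The ratio of Cockcroft-Gault to the under-18 formula is 122 × weight × (1 for males, 0.85 for females) / (0.814 × 0.413 × height), where 122 = 140 − 18 and creatinine cancels. Body sizes are assumed.

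| Height, weight | As written (male, female) | After correction, ÷ 88 (male, female) |
|---|---|---|
| 155 cm, 45 kg | 105, 90 | 1.20, 1.02 |
| 165 cm, 60 kg | 132, 112 | 1.50, 1.27 |
| 180 cm, 80 kg | 161, 137 | 1.83, 1.56 |

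This reaches many patients: 192 weeks is 192 × 7/365.25 = 3.68 years, so anyone aged about 14.3 or older at randomization turns 18 by Week 192.

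**Step 5. Is the adult line affected too?** No. At 18 years, 60 kg and 61.6 micromol/L (assumed values), Cockcroft-Gault as printed gives 122 × 60/(0.814 × 61.6) = 146 mL/min for males, and 124 for females after × 0.85. The mismatch is in the Schwartz line alone.

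**The case against.** The arithmetic is not in dispute. The case against is about weight and reach.

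- **It is a unit label in one descriptive variable of an uncontrolled, supportive report.** True. Serum creatinine, BUN and uric acid have their own summaries and PCSAs, and the protocol's expedited reporting of acute renal failure does not use this derivation. The error over-flags; it does not make a case unflagged. That limits the severity, but the clearance outputs would still be unusable.
- **Anyone would notice clearances near 1 on the first data run.** Probably, since the SAP names the formula and gives normal ranges. But the repair would then depart from the written plan without documentation.
- **Baseline might be carried over from the double-blind dataset, derived under a separate SAP not available here.** This is possible, but the present SAP states only one formula for under-18s. If a correctly scaled baseline were mixed with post-baseline values from this formula, every under-18 patient would show a false fall of about 88-fold, so it would not rescue the tables.
- **The corrected values do not sit wholly inside the normal ranges.** Correct. At Appendix A's upper normal creatinine of 1.5 mg/dL, the corrected formula gives 33 (120 cm) to 52 (190 cm), below the flag. Appendix A's two ranges do not match each other at that end. The argument needs only the order of magnitude, which is clear.
- **The step at age 18 exists without the unit error.** The residual 1.02- to 1.83-fold step does, and it rests on the assumed body sizes. A footnote for it is a desirable extra and not part of the correction itself.

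**Conclusion.** The formula is wrong as written: its unit and constant do not belong together, and under-18 creatinine clearance comes out about 88-fold too low. Over Appendix A's normal creatinine range the results are 0.38 to 1.78 mL/min/1.73m², against 33 to 157 with mg/dL. The conclusion that everyone is flagged does not depend on the assumed heights, because escaping the flag needs a creatinine more than 30 times below the lower normal limit (44/1.31 = 34 at 190 cm). The spurious rise at age 18, 90- to 161-fold, does depend on the assumed heights and weights.

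The consequence is conditional on literal programming and is limited to the clearance variable in the open-label report. Relative change among under-18 clearance values is also unaffected, because the constant cancels. Nothing is concluded here about the double-blind analysis. This should be fixed: the error is certain, the affected safety output would be uninformative, and the correction is nearly free.

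**What to change.** In section 2.5.1, state creatinine in mg/dL for the formula with 0.413, and convert from the SI value inside the derivation. This is the cleaner choice because it needs no new constant. If micromol/L is kept, the constant becomes about 36.3 to 36.5 (0.413 × 88.0 = 36.34; 0.413 × 88.33 = 36.48), or 36.6 from the protocol's pair (0.413 × 88.67), and the SAP must fix one value.

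Derive the under-18 clearance summaries, the baseline status and the clearance PCSA from the corrected line. Add a footnote that equation and unit both change at age 18 (mL/min/1.73m² to mL/min), so change from baseline across that age should be marked or shown separately.

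Cost: one SAP line, one derivation in the laboratory dataset and one table footnote.

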## 6 SELECTION OF PATIENTS

### 6.1 NUMBER OF PATIENTS PLANNED

It is planned that a total of approximately 165 children and adolescents of either gender 10 to below 18 years of age will be randomized into the core study to receive either teriflunomide (110 patients) or placebo (55 patients).

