1 OVERVIEW AND INVESTIGATIONAL PLAN

1.1 STUDY DESIGN AND RANDOMIZATION

This is a multicenter, randomized, double-blind, placebo-controlled, parallel-group study followed by an open-label extension period in children and adolescents 10 to 17 years of age with relapsing forms of multiple sclerosis. It consists of:

- A screening period up to 4 weeks
- A double-blind period of up to 96 weeks treatment for each patient
- An open-label period including the remainder of the initial 96 weeks treatment, where applicable, and a 96-week extension, ie, up to a maximum of 192 weeks after randomization
- An optional additional extension period for young patients with teriflunomide until the patients are 18 years old and/or able to switch to commercial product, whichever comes first
- A follow-up period of 4 weeks for patients discontinuing treatment.

After a screening, eligible patients will be randomly assigned to receive either teriflunomide or placebo in a 2:1 randomization ratio (110 teriflunomide and 55 placebo) via Interactive Voice Response System (IVRS). Randomization will be stratified by the country and patient's pubertal status.

The unblinding of this Phase 3 study will be taken place after the core database lock (DBL), which is expected to be done approximately 28 days after the last patient last visit (LPLV) in the double-blind period/core part of the study. An interim clinical study report (CSR) of the open-label period of this study will be planned upon the core DBL.

The data from the placebo-controlled and the open label teriflunomide treatment periods will be the focus of the CSR of their respective phase. Relevant statistical methods/considerations that mainly relate to the analysis of the data from the placebo-controlled period are employed for data analysis of the open-label period. The data from the open label teriflunomide treatment arm are non-controlled and supportive in nature; summary statistics will be provided for efficacy variables and safety data. More details on interim analysis for the interim CSR of the open-label period are provided in [Section 3](#) Interim Analysis.

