2.4.5 Analyses of safety data

The summary of safety results will be presented by treatment patients actually received in the double-blind and open-label period (placebo/teriflunomide and teriflunomide/teriflunomide) and overall treatment group. Baseline values of the double-blind period will be used as the baseline in the safety analysis for the open-label CSR, unless otherwise noted.

General common rules

All safety analyses will be performed on the safety population as defined in [Section 2.3.3](#), unless otherwise specified, using the following common rules:

- Safety data in patients who do not belong to the safety population will be listed separately.
- The baseline value is defined as the last available value before the first intake of IMP in the double-blind period.
- The potentially clinically significant abnormality (PCSA) values are defined as abnormal values considered medically important by the Sponsor according to predefined criteria/thresholds based on literature review and defined by the Sponsor for clinical laboratory tests, vital signs, and ECG (PCSA version dated May 2014 [[Appendix A](#)]).
- PCSA criteria will determine which patients had at least 1 PCSA during the treatment-emergent adverse event period, taking into account all evaluations performed during the treatment-emergent adverse event period, including nonscheduled or repeated evaluations. The number of all such patients will be the numerator for the on-treatment PCSA percentage.
- The treatment-emergent PCSA denominator by group for a given parameter will be based on the number of patients assessed for that given parameter in the treatment-emergent adverse event period by treatment group on the safety population.
- For quantitative safety parameters based on central laboratory/reading measurements, descriptive statistics will be used to summarize results and change from baseline values of the double-blind period by visit and treatment group. Summaries will include the endpoint value and/or the minimum and maximum value. The endpoint value is commonly defined as the value collected at the same day/time of the last administration of IMP in the open-label period. If this value is missing, this endpoint value will be the closest value prior to the last dose intake.

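### Creatinine clearance changes formula and unit when a patient reaches adulthood, so change from a pediatric baseline subtracts two different quantities

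*SAP*

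**What the plan says.** SAP 2.5.1 gives two derivations of creatinine clearance.

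- For the young: "Creatinine clearance (CrCl) value for children up to 18 years old will be derived from body length and plasma creatinine (Scr"), with the equation printed as "For children/adolescents: CrCl (mL/min/1.73m²) = 0.413 x (height [cm] / Scr [μmol/L"]).
- For the rest: "Creatinine clearance value for adults will be derived using the equation of Cockcroft and Gault". This is (140 - age) × weight / (0.814 × creatinine in µmol/L), times 0.85 for females, in mL/min.

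The section adds: "The age collected at the visit will be used". The formula can therefore change within one patient's record.

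For the baseline, SAP 2.4.5 states: "The baseline value is defined as the last available value before the first intake of IMP in the double-blind period". Protocol 6.1 says that "children and adolescents of either gender 10 to below 18 years of age will be randomized into the core study", and SAP 1.1 lets follow-up run "up to a maximum of 192 weeks after randomization".

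Creatinine clearance is listed among the renal function variables in SAP 2.1.4.3. SAP 2.4.5.3 says that summary statistics "of all laboratory variables (central laboratory values and changes from baseline) will be calculated for each visit or study assessment". The one provision in 2.4.5.3 for patients who become adults is that the abnormality (PCSA) criteria change to the adult set. It gives no rule for the change score.

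**The concern.** Everyone enters below 18, so adult-formula values can arise only after baseline. Each such value is then compared with a baseline that rests on height rather than weight and is indexed to body surface. The difference has no single unit, and part of it reflects body size and sex instead of the kidney.

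The proportion of patients on the second formula grows with time since randomization. A by-visit table of mean clearance or mean change can therefore show a trend although no patient's creatinine has moved. A real decline in patients who have turned 18 can be offset in the same row.

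This is separate from the creatinine unit printed with the Schwartz constant and from the switch of PCSA limits. It remains when both are put right.

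**Working it through.** **Inputs from the documents.** Both formulas, and the use of age at the visit (SAP 2.5.1); ages 10 to below 18 at randomization (Protocol 6.1); 192 weeks of follow-up (SAP 1.1); normal pediatric creatinine of 0.5 to 1.5 mg/dL and normal clearance of 80-120 after age 12 (SAP Appendix A).

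**Assumptions.** Heights, weights, a creatinine of 60 µmol/L where a level is needed, and the entry-age distribution. The documents give none of these.

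**1. Scale of the Schwartz constant.** Appendix A pairs 132 µmol/L with 1.5 mg/dL, that is 132/1.5 = 88 µmol/L per mg/dL. As printed, with creatinine in µmol/L, heights of 130-190 cm and creatinine of 44-132 µmol/L give 0.41 to 1.78, nowhere near 80-120. With creatinine in mg/dL the same inputs give 36 to 157, which spans that range. The constant evidently belongs to the mg/dL scale. All steps below make that correction, so they show what is left once it is made. (Uncorrected, a patient of 165 cm and 55 kg with creatinine 60 would go from 1.14 to 137 if male or 117 if female.)

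**2. Step at 18 with creatinine unchanged.** Creatinine cancels from the ratio:

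Cockcroft-Gault / Schwartz = [(140 - 18) × weight / 0.814 × (0.85 if female)] / (0.413 × height × 88.4)

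The conversion factor here is taken as 88.4; using 88 raises each ratio by about 0.5%.

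| Assumed patient | Ratio |
|---|---|
| Female, 160 cm, 45 kg | 0.98 |
| Female, 162 cm, 55 kg | 1.18 |
| Female, 165 cm, 70 kg | 1.48 |
| Male, 170 cm, 50 kg | 1.21 |
| Male, 175 cm, 65 kg | 1.52 |
| Male, 178 cm, 80 kg | 1.85 |

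At 165 cm the two formulas agree only near 40 kg (male) or 47 kg (female).

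**3. One patient.** Male, 175 cm, 65 kg, creatinine 60 µmol/L: Schwartz 106, Cockcroft-Gault 162, a reported change of +56 with no change in creatinine. If his creatinine rises to 90, Schwartz falls from 106 to 71 (-35). The planned calculation gives 108 - 106 = +2.

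**4. Share who have turned 18.** 96 weeks = 96 × 7/365.25 = 1.84 years; 192 weeks = 3.68 years. With uniform entry ages and no dropout:

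- Ages 10-18: 1.84/8 = 23% by 96 weeks and 3.68/8 = 46% by 192 weeks after randomization.
- Ages 13-18: 1.84/5 = 37% and 3.68/5 = 74%.

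The text leaves the exact cut-off open. If the pediatric formula ran until the 19th birthday, one year comes off: 0.84/8 = 10% and 2.68/8 = 33%, or 0.84/5 = 17% and 2.68/5 = 54%.

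**5. Group mean.** Take 165 cm, 55 kg, creatinine 60 throughout, 25% male, conversion factor 88. The steps are +37.4 (male) and +16.8 (female), so the average step is 0.25 × 37.4 + 0.75 × 16.8 = about 22. Mean change is then +5.5, +11 and +16.5 when 25%, 50% and 75% have turned 18.

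**The case against.** The case for leaving this alone is that little depends on it.

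- Serum creatinine is summarised beside clearance, with its own change from baseline, and uses neither formula. Its PCSAs include an adolescent limit of >132 µmol/L and adult limits of ≥150 µmol/L and of 30% and 100% change.
- The clearance PCSAs are absolute in both age sets, so none uses a change across formulas.
- SAP 2.4.5 calls the safety analysis essentially descriptive, with no systematic testing.
- Results are shown by original randomized arm. The two arms should age alike, so the artefact should be broadly similar in both.

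All of this stands, and it limits the reach of the point.

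A reader might infer that renal harm would go unseen in this trial, or that acute renal failure would be missed. The documents do not support that. Protocol 9.8.1 makes renal failure an individual, investigator-reported event, not one detected through a group mean. A reader might also infer that every patient's value rises at 18, but light females show almost no step or a slight fall. Nor is it established that clearance will be plotted: plots are promised only for laboratory parameters of primary interest, and clearance is not named.

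The shares in step 4 count from randomization, whereas open-label visit windows count from the first open-label dose (SAP 2.5.3). They cannot be read straight onto open-label visit rows.

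None of this makes the change score valid. No sentence in the SAP stops the subtraction.

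**Conclusion.** The point holds as an error in a stated rule with a narrow effect. For patients who turn 18, the planned change in creatinine clearance is a weight-based value in mL/min minus a height-based value in mL/min/1.73m². With creatinine constant, the step is about -2% to +85% over the body sizes assumed, and usually upward. Any true renal change is mixed with it, and the group mean drifts as the adult share grows.

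The existence and form of the problem follow from the text alone. Its size rests on assumed heights and weights, its spread over time on assumed entry ages and no dropout, and both on the Schwartz unit having been corrected. Protocol 11.1 aims for about 10% of patients under 13 as one of two alternative targets, so the 13-18 figures are probably nearer than the 10-18 ones.

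Only the by-visit and change-from-baseline summaries of this derived variable are affected. No efficacy result is touched. It should be corrected, but it does not threaten the trial's conclusions.

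**What to change.** In SAP 2.5.1, state that by-visit and change-from-baseline summaries of creatinine clearance use the same formula at baseline and at every visit. Schwartz throughout would do, with the last available height, which the section already allows; this also covers remote visits, where only weight is collected. Alternatively, report change only where baseline and visit share a formula.

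Derive Cockcroft-Gault as a separately named parameter for the adult PCSA categories, with no change from baseline across formulas. State the age cut-off exactly, and correct the creatinine unit in the Schwartz equation at the same time.

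The cost is a sentence or two in the SAP and one extra derivation, with no new data. The small downside of Schwartz throughout is that a pediatric equation is applied to young adults in the longitudinal summary.
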